Study Subject	An individual that has signed a HIPAA form and an IRB approved study consent form
Subject	Individual being considered for enrollment in to the study
UP	Unanticipated Problem

STUDY SYNOPSIS

Title: A clinical study evaluating the safety and efficacy of punctal plug delivery system (Evolute®) of Nepafenac (N-PPDS) compared with a Placebo Punctal Plug Delivery System (p-PPDS) in Controlling Post-Operative Ocular Pain and inflammation in Subjects undergoing Routine Unilateral Cataract Surgery

Sponsor: Mati Therapeutics Inc.

Clinical Phase: 2

Investigational Masked Product: N-PPDS (Nepafenac Punctal Plug Deliver System) is an L-shaped, silicone punctal plug with a drug eluting core that contains nepafenac (active)

Comparator Masked Product: p-PPDS (placebo Punctal Plug Delivery System) is an L-shaped, silicone punctal plug with a drug insert that contains no active ingredient (placebo).

Number of Sites: up to 3 sites in the USA.

Study Population: Approximately 75 qualified subjects (75 eyes) who have given written consent, have met all study inclusion/exclusion criteria and are scheduled to undergo unilateral cataract surgery with the implantation of an intraocular lens (IOL) will be enrolled in to the study.

Study Objectives: To evaluate the safety and ocular efficacy of N-PPDS in controlling post-operative ocular pain and inflammation associated with cataract surgery.

Study Design: This is a Phase 2, multi-center, randomized, parallel-arm, double-masked, placebo-controlled study. One (1) to 2 days prior to their scheduled cataract surgery, each study subject will be randomized (2:1) in to one of two treatment groups:

Group A: A total of 50 study subjects (50 eyes) will have an N-PPDS inserted in the lower punctum of their scheduled surgical eye.

Group B: A total of 25 study subjects (25 eyes) will have a p-PPDS inserted in the lower punctum of their scheduled surgical eye.

All plugs will remain in the study subject's lower punctum for a period of 2 weeks following cataract surgery.

Subject Selection: The following are inclusion and exclusion criteria for a prospective study subject:

Study Inclusion Criteria:

1. A male or female subject in good general health, ≥ 22 years of age at the time of the screening visit
2. A patient must be able to read, comprehend and willing to give HIPAA & informed consent.
3. A woman of child-bearing potential must not be pregnant or lactating, must have a negative pregnancy test at screening and must be practicing an adequate method of birth control. Acceptable methods of birth control include intrauterine device (IUD); oral, dermal ("patch"), implant or injected contraceptives; tubal ligation; and barrier methods with spermicide.
4. A subject has the availability, willingness and sufficient cognitive awareness to comply with exam procedures and able to return for all scheduled study visits
5. A subject with a cataract for which routine phacoemulsification extraction and implantation of an intraocular lens has been planned
6. A subject has a preoperative corneal astigmatism of 3.0 D or less in their scheduled operative eye
7. A subject with clear ocular media other than cataract in their scheduled operative eye
8. A subject has the potential for a post-operative Snellen BCDVA of 20/30 or better in their scheduled surgical eye
9. A subject has a lower puncta that can be dilated to 1.0 mm in their scheduled surgical eye
10. A subject with a dry eye condition being treated with a marketed punctal plug, where the marketed plug will be replaced by a masked study plug.

Study Pre-Operative Exclusion Criteria:

1. A subject with a history of complications, adverse events, trauma or disease in the nasolacrimal area, whether or not it was due to punctal plug wear, including but not limited to dacryocystitis, inflammation or canaliculitis in either eye
2. A subject with structural lid abnormalities (e.g., ectropion, entropion) in their scheduled surgical eye
3. A subject with a puncta >0.9 mm prior to dilation in their scheduled surgical eye
4. A subject experiencing any ocular pain in either eye at the screening visit or on the day the plug is to be inserted
5. A subject with any moderate to severe lid, conjunctival or corneal findings in either eye at the screening visit
6. A subject with any signs of intraocular inflammation (cells/flare) in either eye at the screening visit
7. A subject with a known sensitivity to nepafenac or any inactive ingredient of the punctum plug, silicone, fluorescein, topical anesthetic, or any other products required for study procedures or cataract surgery
8. A subject with a history as a steroid responder
9. A subject with a known or suspected allergy or hypersensitivity to non-steroidal anti-inflammatory drugs (NSAIDs), or to any component of the test article
10. A subject with only one eye with potentially good vision
11. A subject with a known pathology that may affect visual acuity (as determined by the Investigator); particularly retinal changes that affect vision (macular degeneration, cystoid macular edema, proliferative diabetic retinopathy, etc.) in their scheduled surgical eye
12. A subject that has a condition associated with the fluctuation of hormones that could lead to refractive changes
13. A subject with amblyopia or strabismus
14. A subject with capsule or zonular abnormalities with preoperative lens tilt and/or decentration (e.g., Marfan's syndrome), or may affect postoperative centration or tilt of the lens (e.g. pseudoexfoliation syndrome)
15. A subject has a history of ocular trauma in their scheduled surgical eye
16. A subject that has undergone prior intraocular surgery in the scheduled surgical eye within the last 6 months or laser surgery within three months prior to screening
17. A subject with pupil abnormalities (non-reactive, tonic pupils, abnormally shaped pupils, or pupils that do not dilate at least 3.5 mm under mesopic/scotopic conditions) in their scheduled surgical eye.
18. A subject with a corneal abnormality (e.g., stromal, epithelial or endothelial dystrophies) in their scheduled surgical eye
19. A subject with evidence of clinically significant keratoconus in their scheduled surgical eye
20. A subject with evidence of Epithelial Basement Membrane Dystrophy on slit-lamp exam
21. A subject that has been wearing PMMA lenses within 6 months, gas permeable lenses within one month, or extended-wear or daily soft contact lens within 7 days of their scheduled surgery
22. A subject with an inability to achieve keratometric stability for contact lens wearers
23. A subject with a history of chronic/recurrent inflammatory eye disease (e.g., scleritis, uveitis, herpes keratitis) in either eye
24. A subject with uncontrolled glaucoma
25. A subject that requires an LRI or AI procedure before, during or after cataract surgery
26. A subject that may or is expected to undergo surgical intervention prior to or during the study period other than cataract surgery
27. A subject that requires the use of systemic or ophthalmic NSAIDs or corticosteroid medications during the study period, with the exception of a subject who has been prescribed and has been taking a baby aspirin (≤ 81 mg/daily), (Note: All other NSAIDs or corticosteroid medications must be discontinued at least 48 hours prior to the insertion of the punctal plug)
28. A subject that requires the use of systemic or ocular medications that may affect vision, ocular inflammation or pain
29. A subject with an acute or chronic disease, or illness, that would increase risk or confound study results (e.g., autoimmune disease, connective tissue disease, immunocompromised, suspected glaucoma, glaucomatous changes in the fundus or visual field, ocular inflammation, etc.)
30. A subject with an uncontrolled systemic disease: A potential subject in whom therapy for a systemic disease is not yet stabilized will not be considered for entry into the study

31. A subject with diabetes that is poorly controlled
32. A subject currently participating or has participated in another clinical trial within 30 days prior to enrollment.
33. A subject that requires a stent implant during cataract extraction, with the exception of the implantation of the iStent® by GLAUKOS®

Intra-Operative Exclusion Criteria (Surgical Complications):

1. Sulcus-sulcus or bag-sulcus fixation
2. Posterior capsular rupture or zonular dialysis
3. Disruption of anterior hyaloids face
4. Vitreous loss
5. Capsulorhexis tear
6. Floppy iris syndrome
7. Requirement for the use of trypan blue, capsular tension ring or other intraocular device other than the IOL
8. Inability to place IOL in capsular bag
9. Significant anterior chamber hyphema
10. Zonular rupture.

Study Duration: The project study duration is approximately six months. The study is projected to start in the 1st quarter of 2018.

Study Variables: At the study pre-op and each scheduled post-op visits, the following procedures will be performed and recorded:

- a. Uncorrected distance visual acuity testing (Visit 1, 5, 6 and 7 only)
- b. Manifest Refraction (Visit 1, 6 and 7 only)
- c. Slit Lamp Examination [Lid, conjunctiva, cornea, anterior chamber cells and flare (ACCF)]

NOTE: The Investigator that performs the slit-lamp evaluation at Visit 4 (Day 1 post-op) should perform the slit-lamp evaluation at ALL post-op visits

- d. Record the use of permitted concomitant medication(s), alteration in use or addition of any open-label medication(s) during the study period.
- e. Investigator evaluation of ocular pain

NOTE: The Investigator that interviews and record the subject's response to ocular pain at Visit 4 (Day 1 post-op) should interview the subject at ALL post-op visits (Visits 4, 5, 6 and 7).

- f. Assessment of any reported Adverse Events

Additional procedures will be performed and recorded at Visit 1 (Screening/Baseline, Day -30 to -1), Visit 2 (Punctal Plug Insertion Visit, 1-2 days pre-op), Visit 3 (Surgical day, Day 0) and Visit 7 (Final study visit, Day 14 post-op)

- a. Visit 1:

- Grade Cataract Density (scale: 1 to 4)
- Fundus examination
- Evaluation of lower puncta

- b. Visit 2:

- Insertion of masked study punctal plug
- Inspection of the punctal plug via the slit-lamp in addition, performed at each follow-up visit.

NOTE: All NSAIDs or corticosteroid medications, with the exception of a subject who has been prescribed and has been taking a baby aspirin (≤ 81 mg/daily), must be discontinued at least 48 hours prior to the insertion of the punctal plug.

- c. Visit 3:
 - Pupil measurements (prior to and immediately following surgery)
 - Monocular cataract extraction/IOL implantation
 - Indicate the incision Type, Location and Size (mm)
 - Nucleus removal time
 - Ease Cortex removal
 - Effective Phaco Power (Phaco Time and Power)
 - Type of IOL (e.g., monofocal, toric etc.) and lens power
 - Record any surgical complications
 - Subject reported AEs prior to or after surgery
- d. Visit 7:
 - Fundus examination

Study Efficacy Variables:

Primary: Investigator evaluation of study subject post-op ocular pain at visits 4, 5, 6 and 7.

Secondary: Mean anterior chamber scores for cells and flare at visits 4, 5, 6 and 7

Study Safety Variables: Safety outcome measures include

- a. Distance visual acuity
- b. Slit Lamp Examination (Lid, conjunctiva, cornea)
- c. Fundus Examination
- d. Use of concomitant (rescue) medication(s)
- e. Incidents of reported Adverse Events

Sample Size Determination: Since this is a pilot study, no formal sample size estimation was performed.

Schedule of Assessments, Events

EXAM PARAMETERS	v1	v2	v3	v4	v5	v6	v7
Inform Consent/HIPPA	1						
Demographic data/Medical Hx	1 A						
Concomitant Medication	1	2	3	4	5	6	7
Urine Pregnancy Test (if applicable)	1 B						
Subject Randomization to Treatment		2					
Investigator Evaluation of Ocular Pain	1 C	2		4 F	5 F	6 F	7 F
Uncorrected Distance VA	1 C				5	6	7
Manifest Refraction	1 C					6	7
Best-Corrected Distance VA	1 C					6	7
Slit Lamp Examination	1 C			4 F	5 F	6 F	7 F
Insertion of Masked Punctal Plug		2					
Inspection of Masked Punctal Plug		2 D	3 E	4 D	5 D	6 D	7 D
Evaluation of lower puncta	1						
Pupil Measurements			3 G				
Type and Grade Cataract	1						
Monocular Cataract Extraction/IOL Implantation			3				
Fundus Examination	1						7
Removal of Masked Punctal Plug							7 H
Adverse Event Recording		2	3	4	5	6	7

Keys to Abbreviations:

- A = Prior 12 months
- B = Pregnancy test (women of childbearing potential)
- C = Evaluation of Both Eyes
- D = Evaluation using slit-lamp
- E = Visual inspection after surgery
- F = Investigator that performs the slit-lamp and/or ocular pain evaluation
at Visit 4 (Day 1 post-op) should perform ALL post-op visit evaluations
- G = Measurement to occur prior to surgery and immediately after surgery
- H = All masked punctal plugs must be removed at the subject last visit

Visit Schedule:

- v1 = Day -30 to -1
- v2 = 1 to 2 days prior to surgery
- v3 = Surgery Day
- v4 = 1 day post-op
- v5 = 3 ± 1 days post-op
- v6 = 7 ± 1 days post-op
- v7 = 14 ± 2 days post-op

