5 STUDY ENROLLMENT AND WITHDRAWAL

5.1 Subject Inclusion Criteria

The following are inclusion criteria for a prospective study subject:

1. A male or female subject in good general health, ≥ 22 years of age at the time of the screening visit
2. A patient must be able to read, comprehend and willing to give HIPAA & informed consent.
3. A woman of child-bearing potential must not be pregnant or lactating, must have a negative pregnancy test at screening and must be practicing an adequate method of birth control. Acceptable methods of birth control include intrauterine device (IUD); oral, dermal ("patch"), implant or injected contraceptives; tubal ligation; and barrier methods with spermicide.

4. A subject has the availability, willingness and sufficient cognitive awareness to comply with exam procedures and able to return for all scheduled study visits
5. A subject with a cataract for which routine phacoemulsification extraction and implantation of an intraocular lens has been planned
6. A subject has a preoperative corneal astigmatism of 3.0 D or less in their scheduled operative eye
7. A subject with clear ocular media other than cataract in their scheduled operative eye
8. A subject has the potential for a post-operative Snellen BCDVA of 20/30 or better in their scheduled surgical eye
9. A subject has a lower puncta that can be dilated to 1.0 mm in their scheduled surgical eye.
10. A patient with a dry eye condition being treated with a marketed punctal plug, where the marketed punctal plug will be replaced by a masked study plug.

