5.2 Subject Pre-Operative Exclusion Criteria

The following are pre-surgical exclusion criteria for a prospective study subject:

1. A subject with a history of complications, adverse events, trauma or disease in the nasolacrimal area, whether or not it was due to punctal plug wear, including but not limited to dacryocystitis, inflammation or canaliculitis in either eye
2. A subject with structural lid abnormalities (e.g., ectropion, entropion) in their scheduled surgical eye
3. A subject with a puncta >0.9 mm prior to dilation in their scheduled surgical eye
4. A subject experiencing any ocular pain in either eye at the screening visit or on the day the plug is to be inserted
5. A subject with any moderate to severe lid, conjunctival or corneal findings in either eye at the screening visit
6. A subject with any signs of intraocular inflammation (cells/flare) in either eye at the screening visit
7. A subject with a known sensitivity to nepafenac or any inactive ingredient of the punctum plug, silicone, fluorescein, topical anesthetic, or any other products required for study procedures or cataract surgery
8. A subject with a history as a steroid responder

9. A subject with a known or suspected allergy or hypersensitivity to non-steroidal anti-inflammatory drugs (NSAIDs), or to any component of the test article
10. A subject with only one eye with potentially good vision
11. A subject with a known pathology that may affect visual acuity (as determined by the Investigator); particularly retinal changes that affect vision (macular degeneration, cystoid macular edema, proliferative diabetic retinopathy, etc.) in their scheduled surgical eye
12. A subject that has a condition associated with the fluctuation of hormones that could lead to refractive changes
13. A subject with amblyopia or strabismus
14. A subject with capsule or zonular abnormalities with preoperative lens tilt and/or decentration (e.g., Marfan's syndrome), or may affect postoperative centration or tilt of the lens (e.g. pseudoexfoliation syndrome)
15. A subject has a history of ocular trauma in their scheduled surgical eye
16. A subject that has undergone prior intraocular surgery in the scheduled surgical eye within the last 6 months or laser surgery within three months prior to screening
17. A subject with pupil abnormalities (non-reactive, tonic pupils, abnormally shaped pupils, or pupils that do not dilate at least 3.5 mm under mesopic/scotopic conditions) in their scheduled surgical eye.

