5.5.1.3 Reason for Disqualification

A study subject will be disqualified from the study if there was a failure to obtain written informed consent or HIPAA Authorization, improper entry (did not meet all inclusion/exclusion criteria), had a positive pregnancy test (after Visit 1).

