7.1 Protocol Amendments

Modification of the protocol is prohibited without prior written agreement in the form of a protocol amendment. All amendments will be created by the Sponsor and must be approved by the IRB prior to implementation except when required to mitigate immediate safety risks or when the changes involve only logistical or administrative revisions.

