7.4 Study Visit Schedule

7.4.1 Visit 1: (Screening/Baseline Visit, Day -30 to -1)

A potential study subject qualifications will be assessed according to the inclusion/exclusion criteria listed in the protocol (see [Sections 5.1, 5.2 and 5.3](#)). Prior to undergoing any study-specific procedures, both the study Informed Consent and Authorization for Use/Disclosure of Health Information forms (HIPAA authorization) must be signed by a potential subject who has agreed to participate in the study. During this visit, the following information will be collected/evaluated and recorded in the appropriate sections of the study case report forms for both eyes:

- a. Obtain informed consent and HIPAA release
- b. Record the subject's demographic data and prior 12 month medical history
- c. Record the use of all systemic, topical and/or ophthalmic concomitant medications over the previous 30 days
- d. Urine pregnancy test (if applicable)
- e. Investigator evaluation of ocular pain
- f. Monocular Distance Visual Acuity, Uncorrected and Best-Corrected
- g. Manifest Refraction
- h. Slit-lamp examination
- i. Evaluation of lower punctum (scheduled study eye only)
- j. Type and grade of cataract (scheduled study eye only)
- k. Fundus examination (scheduled study eye only)

A subject who meets all of the study inclusion/exclusion criteria will be scheduled for surgery. Each qualified subject will be scheduled to return to the Investigators office 1 to 2 days before their scheduled surgery for the insertion of the study punctal plug.

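### The only scheduled pregnancy test is at Visit 1, up to 29 days before plug insertion; a repeat test at Visit 2 would be a cheap, minor safety gain

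*Combined protocol and SAP*

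**What the plan says.** Criterion 3, given in the Study Synopsis and again in section 5.1, opens with a condition on status: "A woman of child-bearing potential must not be pregnant or lactating". It then adds that she "must have a negative pregnancy test at screening and must be practicing an adequate method of birth control".

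The urine test is marked at Visit 1 only in the synopsis schedule and in Table 1, and it is item d of the Visit 1 list in section 7.4.1. The Visit 2 list in section 7.4.2 covers ocular pain, plug insertion, plug inspection, adverse events and concomitant medication. It has no pregnancy test. Nor do the lists for Visits 3 to 7, the early exit visit or unscheduled visits.

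Two provisions look past Visit 1. Section 5.5.1.3 disqualifies a subject who "had a positive pregnancy test (after Visit 1"), and lists this separately from improper entry. Exclusion 4 in section 5.2 is assessed at two times, since it removes "A subject experiencing any ocular pain in either eye at the screening visit or on the day the plug is to be inserted".

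For a pregnancy that is found, section 5.5.2.3 covers disqualification, with a safety evaluation and plug removal if a plug was inserted. Section 8.5 covers reporting and follow-up.

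**The concern.** Exposure starts at Visit 2, but the only test supporting the not-pregnant condition may be weeks old by then. A pregnancy that becomes detectable between the two visits would not be found by any scheduled test before the plug goes in. The rule in 5.5.1.3 anticipates a positive result after Visit 1, but nothing in the schedule can produce one.

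What is at stake is avoidable exposure, not the efficacy result. Both nepafenac labels in the appendices (section 8.1 of each) report no adequate studies in pregnant women and reserve use in pregnancy for cases where benefit justifies risk. In the placebo arm the exposure is to the plug and its insertion. A pregnancy found after insertion also means taking the plug out early, and section 6.1.9 advises against removal in the first 24 hours because the cap may tear.

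**Working it through.** The plan gives no figure for the interval from test to insertion, so there is none to reproduce. The steps below use the visit windows and, where the documents are silent, stated assumptions.

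**1. Interval from test to insertion.** Visit 1 is Day -30 to Day -1; Visit 2 is Day -2 or Day -1.
- Longest: -1 - (-30) = 29 days (28 if insertion is on Day -2).
- Shortest: 0 days, if both visits fall on the same day. The windows allow this, but 7.4.1 has the subject come back for insertion, so at least 1 day is likelier.

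**2. Time on the plug.** Visit 7 is Day 12 to Day 16.
- Shortest: Day -1 to Day 12 = 13 days. Longest: Day -2 to Day 16 = 18 days.
- From the only test to the latest scheduled removal: 28 + 18 = 29 + 17 = 46 days.

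**3. Pregnancies a Visit 2 test would newly detect.** Formula: women × annual failure rate × interval / 365. The documents give neither the number of women of child-bearing potential nor a failure rate. I assume 0 to 5 women and 1% to 20% a year.
- No such women, or a same-day test: 0.
- Five women, 14 days: 5 × 0.01 × 14/365 = 0.002; 5 × 0.20 × 14/365 = 0.04.
- Five women, 29 days: 5 × 0.01 × 29/365 = 0.004; 5 × 0.20 × 29/365 = 0.08.
- N-PPDS share of the last line, at 2:1: × 2/3 = 0.003 to 0.05.

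**4. What the repeat test would still miss.** I assume a pregnancy becomes detectable 7 to 14 days after it begins. Among pregnancies present at insertion but missed at Visit 1, the share caught is interval / (interval + lag).

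| Interval | Lag 14 days | Lag 7 days |
|---|---|---|
| 0 days | 0% | 0% |
| 7 days | 7/21 = 33% | 7/14 = 50% |
| 14 days | 14/28 = 50% | 14/21 = 67% |
| 29 days | 29/43 = 67% | 29/36 = 81% |

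Still unseen at insertion with five women: 5 × 0.01 × 7/365 = 0.001 to 5 × 0.20 × 14/365 = 0.04. Pregnancies that begin during the 13 to 18 days of plug wear are not addressed at all.

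**5. Size of the exposure.** The N-PPDS holds 204 micrograms (section 6.1.2). The 0.1% drops contain 1 mg/mL and are given three times daily (Appendix 4). With an assumed drop of 30 to 50 microlitres, the daily dose is 90 to 150 micrograms. The whole plug load therefore equals 204/150 = 1.4 to 204/90 = 2.3 days of labelled drops.

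**6. Animal data.** Appendix 4, section 8.1, reports no evidence of teratogenicity in rats or rabbits at oral doses up to 10 mg/kg/day, which is 80 to 2400 times human plasma exposure with the drops, depending on species and on parent drug or metabolite. Reduced fetal survival in rats occurred at maternally toxic doses.

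**The case against.** The strongest reply is that nothing here is inconsistent. Criterion 3 places the test at screening and the schedules do the same. Required contraception covers the interval, and 5.5.1.3, 5.5.2.3 and 8.5 say what to do if a pregnancy comes to light. A rule for an event learned from the subject or from an unscheduled test is not defective for lacking a scheduled one; 8.5 works the same way. All of that stands. A reader might infer that the plan breaches its own criterion, or that 5.5.1.3 is a dead rule. The documents support neither reading.

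Exclusion 4 is also a weak precedent. Pain is the primary endpoint, so a pain-free start serves efficacy, while exclusions 5 and 6 are fixed at screening. That stands too. Exclusion 4 shows only that an eligibility check on insertion day is already part of the visit.

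The benefit is close to zero on the figures above, and the number of women and the failure rate are assumptions. This limits the point to minor. It does not remove it, because the cost of testing falls along with the number of women to be tested.

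One might also want 5.5.1.3 reworded to cover only a positive test after plug insertion. That would again leave the rule with no scheduled trigger, and it is not needed. A study subject is defined as "An individual that has signed a HIPAA form and an IRB approved study consent form", so the rule can already apply at Visit 2, and 5.5.2.3 requires plug removal only if a plug was inserted.

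**Conclusion.** The point holds as a minor, inexpensive safety improvement. The interval of up to 29 days and the absence of any scheduled test after Visit 1 follow directly from the documents. The benefit does not: 0 to 0.08 pregnancies newly detected rests on the assumed 0 to 5 women, 1% to 20% annual failure and intervals of 0 to 29 days.

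Three stronger conclusions are tempting and should not be drawn.
- The repeat test does not close most of the risk: the share caught runs from 0% to 81% depending on interval and lag, and plug wear is untouched.
- The label's late-pregnancy warning is not engaged by a pregnancy that begins after Visit 1, because removal is at most 46 days later.
- The randomized comparison is not affected.

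**What to change.** - Keep the Visit 1 test.
- In section 7.4.2 and both schedules, add a repeat urine test for women of child-bearing potential at Visit 2, before the subject number is assigned and the plug inserted. Skip it if Visit 1 is the same day. Testing before assignment also avoids spending a number on the randomization list (section 10.6.1) on someone who would be disqualified and replaced.
- Amend criterion 3 in the synopsis and in section 5.1 to require a negative test at screening and again before insertion.
- Leave 5.5.1.3 as worded. A positive Visit 2 test then triggers it, no plug is inserted, and 5.5.2.3 applies. Sections 7.4.1 and 8.5 need no change.

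The cost is 0 to 5 dipsticks under the assumption above, of a type already in use, plus one CRF field and a short amendment. Under section 7.1 an amendment "must be approved by the IRB prior to implementation except when required to mitigate immediate safety risks" or for purely logistical or administrative changes. This change is neither, so it needs IRB approval first. No visit or invasive procedure is added. Very early pregnancies, and those that begin while the plug is in place, would still be missed.
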